Pupil size (mm, OD)	5.51 ± 1.74	6.55 ± 1.12	6.82 ± 0.61	0.04
Pupil response	3.0 ± 0.0	2.8 ± 0.5	1.1 ± 0.9	<0.01
Reading speed (words per second)	3.36 ± 0.55	3.16 ± 0.54	3.25 ± 0.45	0.12
Near point of convergence (cm)	6.8 ± 2.4	7.0 ± 2.2	8.0 ± 3.2	0.25

We plan to examine a wider range of objective measures of visual function and symptoms than previous investigations, including investigate the changes in vision, pupil size, the ability to focus the eyes for near work, reading speed, comfort of the drops, subjective visual effects, presence and severity of headaches, and whether or not someone would be willing to take the drops long-term if they delayed the onset of nearsightedness.

III. Procedures

A. Research Design

This is a prospective cohort study in which we will compare pre-treatment measures to post-treatment measures after taking the treatment for approximately one week. The subjects will serve as their own controls. This will allow us to see the changes to be expected while taking the eye drop. Because the half-life of the drug is approximately 4 hours and maximum cycloplegia (eyes can't focus for near work) occurs in less than one hour, a longer period of time is not required.

B. Sample

We will examine adults between the ages of 21 and 30 years. We are not examining the effects in children because adults will give a more accurate description of the side effects they experience than children. Because children typically complain less about eye comfort and vision issues than adults,³ we strongly believe that we will obtain data that would be considered the worst case scenario for children. The specific entry criteria are listed in Table 3.

Table 3. Entry criteria

Age	21 to 30 years, inclusive
Accommodation	No known history of accommodative issues or therapy

All subjects in the age range specified with no known accommodative (focusing) issues will undergo consent and be enrolled.

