Most of this experiment is hypothesis generating, but we can estimate a sample size based on a two measures, assuming $\alpha = 0.05$ and power = 80%. We aim to detect a change in pupil size of 1.0 mm because this is approximately what was reported in previous studies and what may begin to be clinically meaningful. We conservatively estimate a SD of change of 1.0. We also aim to detect a change in visual acuity of 0.1 logMAR, which is one line of visual acuity, a clinically meaningful change, with a standard deviation change of 0.2. The sample size required for pupil size is eight subjects and the sample size for visual acuity is 31 subjects. We will aim to enroll a sample sufficient to detect both the pupil size and visual acuity change. Assuming a 10% drop out rate, we estimate a sample size of 35, and we include five extra subjects who may be ineligible, for a total sample size of 40 subjects.

C. Measurement / Instrumentation

Manifest Refraction

This is a standard clinical procedure used to measure glasses prescriptions during clinical examinations. Cycloplegic autorefraction, the standard measure of eye prescription in many studies, is not necessary because we are not measuring the change in prescription over time.

Phoria

We will measure phoria at near in order to determine whether low concentration atropine affects how the two eyes work together. Modified Thorington is a more repeatable and less subjective method of measuring phoria than alternating cover test.

Visual Acuity

We will measure the high contrast (black letters) visual acuity at distance and near and the low contrast (grey letters) at distance using logMAR visual acuity charts and scoring on a letter basis. These measures of vision are standard protocols for vision research.

We will measure the pupil size with the NeuroOptics VIP-200 Pupillometer (NeuroOptics, Inc., Irvine, CA) in bright and dim light. For the dim light condition, the subject will stand with his or her back toward the wall-mounted visual acuity chart with the room lights off except for the incandescent lamp pointed straight down over the examination chair at the opposite end of the room. For the bright condition, the subject will stand with his or her back toward the wall-mounted visual acuity chart, and the visual acuity chart illumination should be turned on and be the same as when taking visual acuity measurements (approximately 75 – 120 cd/m² or 9.3-9.9 EV).

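### The sample sizes of 8 and 31 are normal-approximation figures and fall short of 80% power for the planned paired t-test; the pupil SD of 1.0 mm is not shown to be conservative

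*Combined protocol and SAP*

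**What the plan says.** Section III.B (Sample) sets out the calculation "assuming $\alpha = 0.05$ and power = 80"%. It does not state a formula or whether the test is one- or two-sided. Two targets are given:

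- Pupil size: "We aim to detect a change in pupil size of 1.0 mm", with the variability described as "We conservatively estimate a SD of change of 1.0".
- Acuity: "We also aim to detect a change in visual acuity of 0.1 logMAR", "with a standard deviation change of 0.2".

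The result is "The sample size required for pupil size is eight subjects and the sample size for visual acuity is 31 subjects". The sample must serve both targets, so acuity governs. A 10% dropout allowance takes 31 to 35, and five further subjects who may prove ineligible take the total to 40. The same section limits entry to age and known accommodative history, and adds: "All subjects in the age range specified with no known accommodative (focusing) issues will undergo consent and be enrolled".

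Section III.F (Data Analysis) plans repeated measures t-tests for normally distributed variables and Wilcoxon signed-rank tests for the others.

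Table 2 (section II) reports an earlier five-day study of 0.01% atropine. The pupil row gives 5.51 ± 1.74 on Day 1, 6.55 ± 1.12 on Day 3 and 6.82 ± 0.61 on Day 5. For distance acuity the ± values are 0.10, 0.07 and 0.05. No SD of change and no correlation is given.

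**The concern.** A sample size should be computed for the test that will be run. The normal approximation treats the SD of change as known. The paired t-test estimates it, which costs power in small samples, most visibly at n = 8. The 31 has a second defect: 31.40 was rounded down.

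The hypothesis in section I is that pupil size will change and that nothing else will change to a clinically meaningful degree. The expected acuity result is therefore a null one, and readers will weigh it by the stated power. That makes the acuity figure worth getting right.

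The pupil SD raises a different issue. To call an assumption conservative is to say that the true value is probably smaller. The only variability data in the protocol should support that, and for the contrast closest to the planned one week of treatment they point the other way.

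**Working it through.** **Inputs.** From section III.B: alpha 0.05, power 80%; pupil change 1.0 mm with SD 1.0 (standardised effect d = 1.0); acuity change 0.1 logMAR with SD 0.2 (d = 0.5). From section III.F: paired t-test. Two-sided testing is my assumption, checked in step 1.

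**1. Reproducing the plan's figures.** Normal approximation: n = ((1.960 + 0.8416)/d)².

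- Pupil: 2.8016² = 7.85, giving 8.
- Acuity: 7.85/0.25 = 31.40, which is 31 to the nearest whole number and 32 rounded up.
- Dropout: 31/0.9 = 34.4, giving 35; 35 + 5 = 40.

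One-sided alpha gives 7 and 25 by the normal formula, or 8 and 27 by the t-test. Neither pair is 8 and 31, so the two-sided normal approximation is the consistent reading. Even on that approximation, 31 subjects give 79.5% power for acuity.

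**2. Power of the planned test.** Noncentral t with n − 1 degrees of freedom and noncentrality d√n, two-sided 0.05:

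| Outcome | n | Power |
|---|---|---|
| Pupil, SD 1.0 | 8 | 68.1% |
| Pupil, SD 1.0 | 9 | 74.8% |
| Pupil, SD 1.0 | 10 | 80.3% |
| Acuity, SD 0.2 | 31 | 76.8% |
| Acuity, SD 0.2 | 32 | 78.2% |
| Acuity, SD 0.2 | 33 | 79.5% |
| Acuity, SD 0.2 | 34 | 80.8% |
| Acuity, SD 0.2 | 36 | 83.1% |

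The t-test needs 10 and 34.

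**3. Evaluable subjects out of 40.** If all five extras are ineligible and 10% of the rest drop out, 35 × 0.9 = 31.5, so 31 or 32 remain and acuity power is 77% to 78%. If nobody enrolled is ineligible, 40 × 0.9 = 36 remain and power is 83%.

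**4. Pupil SD against Table 2.** Assume that the ± values are SDs, that the same subjects were measured on each day, and that Day 1 is the reference. With correlation r between days, SD of change = √(s₁² + s₂² − 2·r·s₁·s₂), which is never below |s₁ − s₂|.

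Day 1 to Day 5 (1.74 and 0.61), the contrast closest to one week:

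| r | SD of change | n for 80% (t-test) | Power at n = 31 |
|---|---|---|---|
| 1 | 1.13 | 13 | 99.7% |
| 0.5 | 1.53 | 21 | 94% |
| 0 | 1.84 | 29 | 83% |

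An SD of 1.0 would need r = (1.74² + 0.61² − 1)/(2 × 1.74 × 0.61) = 1.13, which is impossible. Allowing for rounding in the table, the lower bound is 1.735 − 0.615 = 1.12.

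Day 1 to Day 3 (1.74 and 1.12): the lower bound is 0.62, and an SD of 1.0 is possible if r is at least (1.74² + 1.12² − 1)/(2 × 1.74 × 1.12) = 0.84.

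**5. Acuity SD against Table 2.** For Day 1 to Day 5 the largest possible SD of change, at r = −1, is 0.10 + 0.05 = 0.15, below the planned 0.2. At 0.15, 31 subjects give about 95% power. Any SD up to about 0.192 gives 80% at n = 31.

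**The case against.** The strongest reply is that nothing operational turns on this. The figures follow from a common approximation, the gap is three subjects and about three points of power for acuity, and section III.B itself describes most of the study as hypothesis generating. The pupil figure of 8 never sets the sample: with 31 subjects the pupil test has 99.97% power at SD 1.0. All of this stands and is why the point is minor. It does not make 8 and 31 correct for 80% power.

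A reader might infer that the trial is underpowered, or that it must enrol more. The documents do not support that. The shortfall at SD 0.2 arises only if the ineligibility allowance is used in full and the full 10% also drop out. Entry depends on age and known history, so ineligibility could largely be settled before enrolment, although the protocol does allow for some. The same Table 2 that undercuts the pupil SD also indicates that the acuity SD is generous. That second inference covers distance acuity only; the table has no row for near or low-contrast acuity.

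A reader might also infer that Table 2 rules out a pupil SD of 1.0 altogether. It does not. The 1.13 bound belongs to the Day 1 to Day 5 contrast. The protocol does not label the ± values, does not say that Day 1 preceded the first drop, and gives no sample size or lighting for that study. Nor is 1.84 an upper limit: negative correlations would give more (SD 2.11 and 72% power at n = 31 for r = −0.5), though for repeated measures on one eye they are implausible.

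**Conclusion.** Wrong as written; minor. The required numbers for the planned two-sided paired t-test at the plan's own SDs are 10 and 34. The stated 8 and 31 deliver 68.1% and 76.8% instead of 80%.

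For the 40 planned subjects, acuity power at SD 0.2 lies between about 77% and 83%, according to how many of the five extras are lost. If Table 2's distance-acuity spread applies, it is higher.

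The description of the pupil SD as conservative is unsupported. Under the assumptions in step 4, the Day 1 to Day 5 change has an SD of at least 1.13 mm, and Day 1 to Day 3 allows 1.0 only with a correlation of about 0.84 or more. This does not threaten the pupil comparison, which keeps at least 83% power at 31 subjects for any r of zero or above.

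**What to change.** Reword the sample-size paragraph in section III.B:

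- Name the method (two-sided paired t-test) and restate the required numbers as 10 for pupil size (SD 1.0) and 34 for acuity (SD 0.2).
- Keep the total of 40 and give acuity power at SD 0.2 for both outcomes of the allowance: 77% with 31 evaluable and 83% with 36 evaluable.
- Remove the claim that the pupil SD is conservative, or replace it with the Day 1 to Day 5 range and its assumptions: SD 1.13 to 1.84 for r from 1 to 0, requiring 13 to 29 subjects.

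The cost is one paragraph of rewording. Enrolment, procedures and analysis do not change. The only downside is a slightly less favourable stated power in the worst case.

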A detailed target on a stick will be too near the eyes to read the letter. The stick will be pulled away from the subject until the subject reads the letter. The distance between the forehead and the stick will be measured to determine the ability to focus.

While wearing full vision correction, the prescription will be measured ten times while looking at distance target using the Grand Seiko WAM-5500 Binocular Autorefractor/Keratometer (AIT Industries, Bensenville, IL). A target will then be placed at 33 cm, and the subject will be told to keep the target clear while measuring the prescription five times. The prescription at distance will be subtracted from the prescription at near, and that result will be subtracted from 3.0 D, which is the focusing demand.

Reading Speed will be measured using the Rate of Reading Test. This test contains the same 15 simple words, repeated on each line and presented in random order. It is meant to serve as a test of reading speed pre- and post-intervention.

Subjects will view a card held at 40 cm. Flippers with +2.50 D lenses on one side and -2.50 D lenses on the other side will be placed in front of the subject, and the subject will report when the letters become clear. The lenses will be flipped, and the subject will again report when the print is clear. This will be continued for 1 minute, and the number of flips will be counted. This is a routine clinical measure of the ability to change focus from distance to near.

We will survey subjects about light sensitivity, drop comfort, likelihood of taking the drop to delay the onset of nearsightedness, vision symptoms, headaches, and comfort of the proparacaine eye drop and an artificial tear eye drop (for comparison of drop comfort to low concentration atropine). We will use the following format to collect survey data (using different questions and anchors as necessary):

1	2	3	4	5	6	7	8	9	10
Good									Perfect

We will measure the pressure in the eye using a Tonopen, a clinical measure that is performed during routine eye examinations. This requires a drop of 1% proparacaine in each eye to numb the eye. This drop is also used during routine eye examinations.

D. Detailed Study Procedures

Manifest Refraction

The examiner will measure glasses or perform retinoscopy to get a starting point for the refraction. The refraction will be performed using Jackson crossed cylinder, binocular blur balance, and maximum-plus-to-maximum-acuity to obtain the final refraction.

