Press the OD button to activate the unit. Bring the unit up in front of the subject's right eye with the eye cup resting against the subject's face and hold down the OD button continuously. When the pupil is marked with a green circle, release the button to initiate the measurement. Hold the unit still during the few seconds of the measurement. Take care that the eyelids do not cover the pupil. If the green measurement circle was not centered over the pupil, delete the measurement by using the Eraser icon at the right side of the three-icon Tool menu. Repeat the measurement until the green measurement circle is centered over the pupil. Record the pupil size to the nearest 0.1 millimeter on the examination form. Repeat steps 6-9 while the lights are in the mesopic condition.

Focusing Ability

A letter target on a stick is placed against the nose, in front of the eyes. Tell the subject the stick will be moved slowly away until the subject can first read the letter correctly. The subject should say the letter as soon as s/he can read it. The distance from the forehead to the stick is measured to the nearest cm and recorded.

Lag of Focus

Place the manifest correction used for visual acuity in a trial frame, minimizing the number of lenses used in the trial frame. Place an occluding trial lens in the trial frame well over the left eye so that the subject will only view targets with the right eye. Place the 33cm near rod in the central slot to measure accommodative lag in primary gaze only. Place the subject's chin on the chinrest and forehead against the forehead rest. Obtain a view of the eye on the screen. The white keratometry circle should be in focus. Centered the pink reticule within the white keratometry ring. Encourage the subject to keep the letters as clear as possible throughout the measurement and have the subject focus on a specific letter to ensure the subject is attentive and accommodating. Obtain at least five readings without the "retry" message. When in doubt, take additional measurements to ensure that at least 5 measurements exist. Press Print and tape the printout in the location indicated on the exam form.

Reading Speed

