We will measure the potential side effects of low concentration atropine in adults rather than children, although children will ultimately receive low concentration atropine for myopia control. We are not examining the effects in children because adults will give a more accurate description of the side effects they experience than children. Because children typically complain less about eye comfort and vision issues than adults,³ we strongly believe that we will obtain data that would be considered the worst case scenario for children.

We will use a pre- post-test format in order to examine the changes to be expected over a short period of time. The first week of experience will typically guide the likelihood of long-term commitment to the treatment.^{4,5} We therefore want to know how much administration of low concentration atropine will have on subjects' vision.

F. Data Analysis

We will perform repeated measures t-tests to determine whether there are significant changes over time for normally distributed variables and Wilcoxon signed-rank tests to determine whether there are significant changes over time for non-normally distributed variables.

IV. Bibliography

4. Lang JM. The use of a run-in to enhance compliance. *Stat Med*. 1990;9(1-2):87-93; discussion 93-85.

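### Read literally with signed readings, the lag-of-focus rule scores a worsened lag as an improvement, and the detailed procedure omits the distance readings that the rule needs

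*Combined protocol and SAP*

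**What the plan says.** The autorefractor paragraph of III.C sets out the measurement and the score. With full correction worn, "the prescription will be measured ten times while looking at distance target using the Grand Seiko WAM-5500"; five readings are then taken with a target at 33 cm. The score follows: "The prescription at distance will be subtracted from the prescription at near, and that result will be subtracted from 3.0 D", where 3.0 D is identified as the focusing demand. The paragraph does not say how the readings are signed, or whether a larger score means better or worse focusing.

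III.D, under Lag of Focus, gives the examiner's steps: correction in a trial frame, left eye occluded, then "Place the 33cm near rod in the central slot to measure accommodative lag in primary gaze only", one set of at least five valid readings, and the printout taped to the exam form. It mentions neither a distance target nor the ten distance readings, and it does not refer back to III.C.

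For the analysis, III.F says: "We will perform repeated measures t-tests to determine whether there are significant changes over time for normally distributed variables", with Wilcoxon signed-rank tests for the other variables.

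**The concern.** Lag is demand minus response. The response is how much more minus the eye reads at near than at distance, which in signed dioptres is distance minus near. III.C forms near minus distance, which is negative for an eye that focuses. Subtracting it from the demand adds the response instead of removing it.

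At stake is the direction of a side-effect result. The ability to focus for near work is a listed objective (section I), and the study's hypothesis is that nothing except pupil size will change to a clinically meaningful degree. A reversed score would report poorer focusing as better focusing.

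The second problem does not depend on signs. An examiner who works from III.D alone finishes without one of the two terms in the formula. A sign can be corrected later, but a reading that was never taken cannot be recovered.

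**Working it through.** **Inputs from the protocol.** Target at 33 cm, demand 3.0 D, rule 3.0 − (near − distance) (all III.C).

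**Assumptions, not in the protocol.** Readings are ordinary signed dioptres. Write d for the distance reading through the correction and A for the focusing response, so near = d − A. Illustrative values: A = 2.50, 2.25, 2.00, 1.50 and 1.00 D; d = −0.25, 0 and +0.25 D.

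**The plan's own figure.** 1/0.33 m = 3.03 D, which rounds to the stated 3.0 D. The demand is right.

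**The rule with signed readings.** Near − distance = (d − A) − d = −A. The score is 3.0 − (−A) = 3.0 + A. True lag is L = 3.0 − A, so the score is 6.0 − L, whatever the value of d.

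| Response A (D) | True lag 3.0 − A | Score as written 3.0 + A |
|---|---|---|
| 2.50 | 0.50 | 5.50 |
| 2.25 | 0.75 | 5.25 |
| 2.00 | 1.00 | 5.00 |
| 1.50 | 1.50 | 4.50 |
| 1.00 | 2.00 | 4.00 |

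If the response falls from 2.50 to 2.00 D, true lag rises by 0.50 D (0.50 to 1.00) while the written score falls by 0.50 D (5.50 to 5.00).

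**The rule with unsigned magnitudes.** The score becomes 3.0 − (|near| − |distance|). For d zero or minus, |near| − |d| = A and the lag is correct. For d plus (and smaller than A), |near| = A − d, so the score is 3.0 − A + 2d. At d = +0.25 and A = 2.25 it gives 1.25 D against a true 0.75 D.

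**Effect on the tests.** With signed readings each subject's change is multiplied by −1. The t statistic changes sign and keeps its size, and the two signed-rank sums swap. Two-sided p-values are therefore unchanged. A simulated paired set of 35 subjects (assumed data) agreed: mean change +0.396 D for true lag and −0.396 D for the written score, with |t| = 6.37 and identical two-sided p-values for both tests.

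**Distance readings skipped.** If d is treated as zero and the sign is handled correctly, the computed lag is 3.0 + near = 3.0 + d − A = L + d. With A = 2.25 (true lag 0.75) this gives 0.50 D at d = −0.25 and 1.00 D at d = +0.25. The error in the pre-post change is d(post) − d(pre). It is zero if d is the same at both visits, and +0.50 D if d moves from −0.25 to +0.25.

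**The case against.** The case for leaving this alone has real weight.

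- *The convention is unstated.* The sentence may be a plain-language account of demand minus response, read as amounts of minus power. On that reading the rule works for distance readings of zero or minus. So a reader might infer that every lag value will be wrong and reversed, but the documents do not support that as a certainty; it depends on how staff handle the signs. The objection does not clear the text, though. The unsigned reading fails for plus distance readings, and the protocol elsewhere writes lens powers with signs and gives phoria an explicit sign rule. No single reading of the sentence is right for every subject.
- *The damage can be undone and would probably be seen.* The score is an exact mirror of the lag, and III.D keeps the printouts. Any focusing at all gives a score above the 3.0 D demand, which should look odd. This stands, and it limits the severity.
- *The distance readings are in the plan.* III.C requires them, nothing says that III.D replaces III.C, and subjects are their own controls, so a constant residual error cancels from the change. This also stands. A reader might infer that the study will never take distance readings; the documents show only that the two sections do not match.
- *Lag carries little weight in the design.* The protocol calls most of the work hypothesis-generating and sizes the study on pupil size and visual acuity. Lag is one of three focusing measures, and this error does not touch the stick test or the flippers. This is correct.

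**Conclusion.** The point holds in a limited form. With ordinary signed readings, which is an assumption but the natural one, the III.C rule gives 6.0 D minus the true lag: wrong in level and opposite in direction. The absolute size of the change, the two-sided p-values and the sample size are unaffected. It would be wrong to infer that the planned tests are invalid or that data are lost through the sign, since the correct lag can be recomputed from the raw readings provided the distance readings were taken.

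The mismatch between III.C and III.D is a separate inconsistency. If examiners followed III.D alone, the lag level would be off by the residual refractive error (−0.25 to +0.25 D over the assumed range), and the change would be off only by the difference in that error between visits.

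Severity: minor to moderate. The rule is wrong as written, but for a secondary, exploratory measure.

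**What to change.** In III.C, state that readings are signed dioptres and write lag = 3.0 D − (mean distance reading − mean near reading), with a larger positive value meaning more lag. With the illustrative responses of 2.50 and 2.00 D this gives 0.50 and 1.00 D whatever the distance reading, so the score rises as focusing worsens.

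In III.D, Lag of Focus, add the ten distance-target readings before the near rod is placed, or cross-refer to III.C for them, at both visits.

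If data have already been collected, recompute lag from the printouts and check that distance readings exist for both visits.

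The cost is a corrected formula with its convention, plus one procedure sentence. No measurement is added beyond what III.C already requires.

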Side Effects of Atropine (SEA) Study

NCT03593044

November 23, 2021

Research Protocol
Side Effects of Atropine (SEA) Study
Version 1.0

I. Objectives

The purpose of this study is to determine whether there are any changes in subjective or objective measures of eye comfort or vision. Specifically, we will monitor for the following changes:

1. High contrast distance, high contrast near, and low contrast distance visual acuity
2. Pupil size
3. Ability to focus the eyes for near work
4. Reading speed
5. Subjective comfort and vision issues
6. Headaches
7. Intraocular pressure

We hypothesize that pupil size will increase significantly, but no other measures will change clinically meaningfully.

II. Background and Rationale

1.0% atropine is routinely used to dilate pupils and knock out the ability to focus the eyes to see close objects clearly, and it also slows the progression of nearsightedness. Many eye care practitioners are now using 0.01% atropine to slow the progression of nearsightedness because it slows the progression of nearsightedness by 60%¹ to 83%,² and it causes much fewer side effects than 1.0% atropine. One study compared myopia progression and side effects of 0.01%, 0.1%, and 0.5% atropine in children. While 0.5% atropine slowed myopia progression significantly more than 0.01% atropine, there were no other differences in myopia progression over two years, and there were fewer side effects with 0.01% atropine (Table 1), so many eye care practitioners now use 0.01% atropine to slow the progression of nearsightedness.

Table 1. Ocular changes after taking various concentrations of atropine.

	0.01%	0.1%	0.5%	p-value
Accommodative amplitude (D)	-4.6	-10.1	-11.8	<0.001
Pupil size in dim light(mm)	1.15	2.71	3.56	<0.001
Pupil size in bright light (mm)	0.75	2.24	3.11	<0.001
Distance visual acuity (logMAR)	-0.02	+0.01	-0.01	0.44
Near visual acuity (logMAR)	-0.02	+0.06	+0.25	<0.001
Asked for glasses to improve near vision (% yes)	6	61	70	<0.001

Another study examined the changes in visual function and symptoms of young adults while taking daily drops of 0.01% atropine for five days. Only pupil size and pupil response exhibited a significant change over that time period (Table 2).

Table 2. The change in vision function while taking 0.01% atropine for five days.

	Day 1	Day 3	Day 5	p-value
Distance VA (logMAR, OD)	-0.10 ± 0.10	-0.08 ± 0.07	-0.08 ± 0.05	0.55
Near point of accommodation (D)	10.2 ± 1.42	10.0 ± 1.39	9.1 ± 2.12	0.08

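### The near point is one hand reading to a whole centimetre, about the size of the prior adult change, and nothing in the plan withholds the pre-treatment value at the second visit

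*Combined protocol and SAP*

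**What the plan says.** Section III.A sets out a single-group comparison in which "we will compare pre-treatment measures to post-treatment measures after taking the treatment for approximately one week", and adds: "The subjects will serve as their own controls". Everyone takes the drop, in a fixed order.

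The ability to focus for near work is the third of the seven listed objectives. Section III.D (Focusing Ability) has the examiner move a letter target slowly away from the face. The endpoint comes from the subject: "The subject should say the letter as soon as s/he can read it". Then: "The distance from the forehead to the stick is measured to the nearest cm and recorded". No repeat reading is described. No section says whether the pre-treatment value is available to the examiner at the second visit, or whether the same examiner does both visits.

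The hypothesis in Section I is: "We hypothesize that pupil size will increase significantly, but no other measures will change clinically meaningfully". The closest prior evidence in adults is the near-point row of Table 2 in Section II (days 1, 3 and 5, then the p-value): "Near point of accommodation (D) 10.2 ± 1.42 10.0 ± 1.39 9.1 ± 2.12 0.08".

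Other measures are recorded more tightly. Pupil size is read to 0.1 mm against a target change of 1.0 mm. Lag of focus needs at least five autorefractor readings and leaves a record: "Press Print and tape the printout in the location indicated on the exam form".

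**The concern.** For every measure except pupil size, the study expects to report no clinically meaningful change. A coarse measurement, or one that drifts towards its earlier value, makes such a report easier to reach.

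Two features of the near-point measure matter. First, its recording unit is about as large as the change seen in the nearest prior study, which adds avoidable noise. Second, the examiner controls the stick and reads the ruler. If the examiner knows the first value, the second reading may be drawn towards it, and the paired tests in Section III.F cannot tell that from a true absence of effect.

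Blinding to the drug is not available here, because everyone is treated and the enlarged pupil would reveal the visit. Withholding the first reading is available.

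**Working it through.** **Inputs.** Table 2: 10.2 D (SD 1.42) on day 1 and 9.1 D (SD 2.12) on day 5. Table 1: -4.6 D in children on 0.01%. Section III.D: resolution 1 cm. Section III.B: 31 subjects for visual acuity. Assumptions: dioptres = 100/cm measured from the eye (the protocol measures from the forehead and states no conversion), and a pre-post correlation of 0.5 to 0.9 (the documents give none).

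**1. The plan's sample size.** With n = (SD × (1.960 + 0.842)/change)², pupil size gives (1.0 × 2.802/1.0)² = 7.85, stated as 8. Visual acuity gives (0.2 × 2.802/0.1)² = 31.4, stated as 31. Neither calculation uses focusing ability, so this point does not touch the sample size.

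**2. Table 2 in recording units.** 100/10.2 = 9.80 cm and 100/9.1 = 10.99 cm. The difference is 1.19 cm, or about 1.2 recording units. Pupil size has 1.0/0.1 = 10 units across its target change.

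**3. One unit in dioptres.** From 10 to 11 cm: 100/10 − 100/11 = 0.91 D. Against 10.2 − 9.1 = 1.1 D, this is 83%.

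**4. Table 1 in recording units.** Table 1 gives no baseline, so a range is assumed. From 10.2 D: 100/5.6 − 100/10.2 = 8.1 cm. From 16 D: 100/11.4 − 100/16 = 2.5 cm. A change of that size spans several units.

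**5. Honest rounding.** Rounding to 1 cm adds variance 1/12 cm² per reading and 2/12 = 0.167 cm² to a pre-post difference (SD 0.41 cm). Near 10 cm, 1 cm is about 1 D, so this is about 0.167 D². The variance of change without it is 1.42² + 2.12² − 2r(1.42)(2.12) = 6.51 − 6.02r.

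| Assumed r | Variance of change (D²) | Inflation from rounding |
|---|---|---|
| 0.5 | 3.50 | 0.167/3.50 = 4.8% |
| 0.9 | 1.09 | 0.167/1.09 = 15.3% |

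On the mean of 31 subjects, the rounding component is 0.41/√31 = 0.07 cm. It adds noise and does not shift the mean. Reading to 0.1 cm divides the rounding variance by 100.

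**6. Anchoring, as illustration only.** If a fraction of post-treatment readings were recorded as 10 cm instead of 11 cm, the mean loss would shrink by that fraction of 0.91 D: 0.09 D at 10%, 0.23 D at 25%, 0.45 D at 50%. These fractions are assumed and have no source in the documents.

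**The case against.** A reader might infer that a one-centimetre nudge equals the effect the study seeks. The documents do not support this. Section III.B sets target changes for pupil size and visual acuity only, and Section I expects no meaningful change in focusing. The 1.1 D is background data with p = 0.08. A shift of a full centimetre in the mean would also need the same nudge in nearly every subject. This stands.

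A reader might also infer that the examiner sees the pre-treatment value. The documents are silent. What can be said is that no safeguard is written.

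The subject must name the letter correctly, which limits the examiner's discretion. That is true, although the examiner still moves the stick and reads the ruler.

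The direction of any bias is not established. Section II describes what 1.0% atropine does to focusing, so an examiner could equally expect a loss. A pull towards no change is one possibility, and it matters because it is the one that would favour the hypothesis.

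Focusing is also assessed by autorefractor lag and by lens flippers, so this is not the only focusing measure. But lag is taken at a 3.0 D demand, and a fall in the near point from 10.2 to 9.1 D could leave it unaffected. The flipper test measures speed of refocusing. Neither measures the near point.

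Finally, a finer reading does not address anchoring, and a hand-held stick may not support 0.1 cm. Both remarks are fair. The form-handling step deals with anchoring, and the resolution can be set at whatever the ruler supports.

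**Conclusion.** The point holds in a limited form. The near point is a single hand reading whose unit (about 0.9 D near 10 cm) is nearly the whole of the 1.1 D, or 1.2 cm, change in Table 2. A change like that in Table 1 would span several units. Rounding costs about 5% to 15% in the variance of change, given the Table 2 SDs and assumed correlations of 0.5 to 0.9, and leaves the mean unbiased.

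Anchoring is possible because nothing written prevents it, but its size is unknown and its presence is not shown. The dioptre figures rest on measuring from the eye. A constant offset between forehead and eye would cancel in the centimetre difference but not in the dioptre values.

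Priority is low. The protocol describes most of the experiment as hypothesis generating, it names no primary endpoint, and its sample size does not depend on this measure.

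**What to change.** In Section III.D (Focusing Ability), make two changes:

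1. At both visits, record the distance to the nearest 0.1 cm, or to the finest division the ruler supports, instead of the nearest centimetre.
2. Use a separate post-treatment form, and keep the pre-treatment form out of the examiner's sight until the hand-read focusing measure is complete.

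The cost is slightly more care in reading the ruler and handling forms. No extra staff, visits or procedures are needed. Averaging repeat readings would reduce noise further but takes more examination time, so it is optional.
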